Table 3-6 Study VX16-445-001: Schedule of Assessments for Parts D1 and D2

Event/Assessment ^a	Screening	Treatment Period					ETT Visit ^b	Safety Follow-up 28 (± 7) Days After Last Dose
		Period 1			Period 2			
	Days -28 to -1	Day 1 ^c	Day 8 for Part D1 only (± 1 day)	Day 15 (± 2 days)	Day 29 (± 2 days)	Period 2 Visit ^d		
Serum chemistry and hematology ^g	X	X	X	X	X		X	X
Coagulation ^g	X	X		X	X		X	X
PK sampling ^t		X		X	X	X	X	
TEZ/IVA or placebo dosing ^u		Day 1 through Period 2 Visit						
VX-445 or placebo dosing ^v		Day 1 through Day 29						
AEs, medications ^w , treatments, and procedures	Continuous from signing of the ICF through the Safety Follow-up Visit							

AE: adverse event; CF: cystic fibrosis; CFQ-R: Cystic Fibrosis Questionnaire-Revised; *CFTR*: CF transmembrane conductance regulator gene; [redacted]; ECG: electrocardiogram; ETT: early termination of treatment; FSH: follicle-stimulating hormone; G6PD: glucose-6-phosphate dehydrogenase; ICF: informed consent form; IVA: ivacaftor; PE: physical examination; PK: pharmacokinetic; ppFEV₁: percent predicted forced expiratory volume in 1 second ; TEZ: tezacaftor

^t Blood samples will be collected for the G6PD activity test.
[redacted]

Blood samples will be collected for PK analysis of VX-445, TEZ, M1-TEZ, IVA, and M1-IVA. On the Day 1 Visit, samples will be collected before dosing (0 hours) and at 1, 2, 4, and 6 hours after dosing (relative to the morning dose). On the Day 15 Visit, samples will be collected before dosing (0 hours) and at 1, 2, 4, 6, and 8 hours after dosing. On the Day 29 Visit, a predose sample will be collected before the morning dose of study drug. At the Period 2 Visit, a single predose sample will be collected before TEZ/IVA dosing in the morning. At the ETT Visit, a single blood sample for PK analysis will be collected.

^u On days of scheduled visits, the in-clinic dose of study drugs will be given in the morning, at least 6 hours apart from any other scheduled dose and after all predose assessments are complete. The last dose of TEZ/IVA or placebo in Period 2 will be the morning dose of the Period 2 Visit. See [Section 9.6.2](#) for additional information about study drug administration.

^v On days of scheduled visits, the in-clinic dose of study drugs will be given in the morning, at least 6 hours apart from any other scheduled dose and after all predose assessments are complete. The last dose of VX-445 or placebo in Period 1 will be the morning dose on the Day 29 Visit. See [Section 9.6.2](#) for additional information about study drug administration.

^w Refer to [Section 9.5.2](#) for details.

Table 3-7 Study VX16-445-001: Schedule of Assessments for Part E

Event/Assessment ^a	Screening	Run-in Period		Treatment Period: Period 1			Washout Period		ETT Visit ^b	Safety Follow-up 28 (± 7) Days After Last Dose ^c
	Days -56 to -29	Day -28 (± 1 day)	Day -14 ^d (+ 13 days)	Day 1 ^e	Day 15 (± 2 days)	Day 29 (± 2 days)	Day 43 (± 3 days)	Day 57 (± 3 days)		
Informed consent	X									
Randomization ^f				X						
Demographics	X									
Medical history	X									
CFQ-R ^{g,h}				X	X	X		X		
Weight ⁱ	X	X		X	X	X	X	X	X	X
Height ⁱ	X									
Vital signs ^j	X	X		X	X	X	X	X	X	X
Pulse oximetry ^j	X	X		X	X	X	X	X	X	X
Physical examination ^k	Complete	Abbreviated		Abbreviated	Abbreviated	Abbreviated		Abbreviated	Abbreviated	Complete

^a All assessments will be performed before dosing, unless noted otherwise. Assessments that are collected before and after dosing will only be collected once if study drug is not administered on the day of the visit (i.e., if subject prematurely discontinued study drug treatment).

^b If the subject prematurely discontinues study treatment, an ETT Visit should be scheduled as soon as possible after the decision to terminate study drug treatment. Subjects who prematurely discontinue treatment will also be required to complete the Safety Follow-up Visit. If the ETT Visit occurs 3 weeks or later following the last dose of study drug, the ETT Visit will replace the Safety Follow-up Visit, and a separate Safety Follow-up Visit will not be required. Part E subjects who meet criteria specified in [Section 9.1.2.6](#) will not have a Safety Follow-up Visit.

^d The Day -14 Visit is only required for subjects who are not transitioning directly from at least 14 days of uninterrupted TEZ/IVA treatment. Assessments at this visit may be performed postdose.

^e To be eligible to continue into the Treatment Period, subjects must have stable CF disease and have remained on stable CF medication regimen during the 28 days before the Day 1 Visit AND must not have had an acute non-CF illness within 14 days before the Day 1 Visit. See [Section 9.1.2.4](#).

^f Randomization may occur on the previous day (Day -1 Visit) after all inclusion and exclusion criteria and criteria for entry into the Treatment Period have been confirmed. See [Section 9.1.2.2.2](#).

^g CFQ-R must be completed before the start of any other assessments scheduled at that visit.

^h The predose assessment on the Day 1 Visit may be performed on the previous day (Day -1 Visit) if randomization has occurred.

ⁱ Weight and height will be measured with shoes off.

^j Vital signs and pulse oximetry will be collected after the subject has been seated for at least 5 minutes.

^k Complete and abbreviated PEs are described in [Section 11.7.3](#). Symptom-targeted PEs will occur at any time during the study if triggered by AEs or if deemed necessary by the investigator or healthcare provider.

Table 3-7 Study VX16-445-001: Schedule of Assessments for Part E

Event/Assessment ^a	Screening	Run-in Period		Treatment Period: Period 1			Washout Period		ETT Visit ^b	Safety Follow-up 28 (± 7) Days After Last Dose ^c
	Days -56 to -29	Day -28 (± 1 day)	Day -14 ^d (+ 13 days)	Day 1 ^e	Day 15 (± 2 days)	Day 29 (± 2 days)	Day 43 (± 3 days)	Day 57 (± 3 days)		
Standard 12-lead ECG ^l	X	X		X	X	X	X	X	X	X
Sweat chloride ^{h,m}	X		X	X	X	X	X	X	X	
Spirometry ⁿ	X ^o		X ^o	X	X	X	X	X	X	X
Urinalysis ^h	X	X		X	X	X	X	X	X	X
Pregnancy test (all females of childbearing potential)	Serum	Urine		Urine		Urine		Urine	Serum	Serum
CFTR genotype ^p	X									
FSH ^q	X									
G6PD activity test ^r	X									

^l All standard 12-lead ECGs will be performed after the subject has been seated or supine for at least 5 minutes. On the Days 1 and 15 Visits, ECGs will be collected before dosing and 5 hours (± 1 hour) after dosing. At all other visits, ECGs will be collected before dosing (as applicable). ECGs collected on the Day 1 Visit before dosing will be performed in triplicate.

^m Sweat chloride will be measured in all subjects as described in [Section 11.4.1](#). If the value cannot be determined from the screening test (e.g. due to laboratory error), a sweat chloride value documented in a previous laboratory report may be used to establish eligibility. See [Section 8.2.1](#) (Inclusion Criterion #5) for additional detail.

ⁿ Spirometry may be performed pre- or post-bronchodilator at the Screening Visit. Spirometry will be performed pre-bronchodilator, before the morning dose of study drugs (except at the Day -14 Visit when spirometry may be performed postdose), and should be performed at approximately the same time at every visit. On the Day 1 and Day 15 Visits, spirometry will also be performed 5 hours (± 1 hour) after study drug administration (pre-bronchodilator).

^o The ppFEV₁ assessment for stratification of randomization will be done at the Screening Visit for subjects transitioning directly from at least 14 days of uninterrupted TEZ/IVA treatment. For all other subjects, this assessment will be done at the Day -14 Visit. See [Section 9.1.2.2](#)

^p CFTR genotyping will be performed for all subjects. If the screening CFTR genotype result is not received before the Day -28 Visit, a previous CFTR genotype laboratory report may be used to establish eligibility. However, as outlined in [Section 9.9](#), subjects who have been randomized and whose screening CFTR genotype does not confirm study eligibility must be discontinued from the study, even if a previous CFTR genotype laboratory report was used to establish eligibility.

^q FSH will be measured for any suspected postmenopausal female subjects with at least 12 months of continuous spontaneous amenorrhea.

^r Blood samples will be collected for the G6PD activity test.

Table 3-7 Study VX16-445-001: Schedule of Assessments for Part E

Event/Assessment ^a	Screening	Run-in Period		Treatment Period: Period 1			Washout Period		ETT Visit ^b	Safety Follow-up 28 (± 7) Days After Last Dose ^c
	Days -56 to -29	Day -28 (± 1 day)	Day -14 ^d (± 13 days)	Day 1 ^e	Day 15 (± 2 days)	Day 29 (± 2 days)	Day 43 (± 3 days)	Day 57 (± 3 days)		
Serum chemistry and hematology ^h	X	X		X	X	X	X	X	X	X
Coagulation ^h	X	X		X	X	X			X	X
PK sampling ^t				X	X	X	X		X	
TEZ/IVA dosing ^u		Day -28 through Day 57								
VX-445 or placebo dosing ^v				Day 1 through Day 29						
AEs, medications ^w , treatments and procedures	Continuous from signing of the ICF through the Safety Follow-up Visit									

AE: adverse event; CF: cystic fibrosis; CFQ-R: Cystic Fibrosis Questionnaire-Revised; *CFTR*: CF transmembrane conductance regulator gene; [REDACTED]; ECG: electrocardiogram; ETT: early termination of treatment; FSH: follicle-stimulating hormone; G6PD: glucose-6-phosphate dehydrogenase; ICF: informed consent form; IVA: ivacaftor; PE: physical examination; PK: pharmacokinetic; ppFEV₁: percent predicted forced expiratory volume in 1 second ; TEZ: tezacaftor

^t Blood samples will be collected for PK analysis of VX-445, TEZ, M1-TEZ, IVA, and M1-IVA. On the Day 1 Visit, samples will be collected before dosing (0 hours) and at 1, 2, 4, and 6 hours after dosing (relative to morning dose). On the Day 15 Visit, samples will be collected before dosing (0 hours) and at 1, 2, 4, 6, and 8 hours after dosing. On the Day 29 Visit, a predose sample will be collected before the morning dose of study drug. At the Day 43 Visit, a single blood sample for PK analysis will be collected before the morning dose of TEZ/IVA. At the ETT Visit, a single blood sample for PK analysis will be collected.

^u The last dose of TEZ/IVA will be the morning dose on the Day 57 Visit. See [Section 9.6.2](#) for additional information about study drug administration.

^v The last dose of VX-445 or placebo will be the morning dose on the Day 29 Visit. See [Section 9.6.2](#) for additional information about study drug administration.

^w Refer to [Section 9.5.2](#) for details.

Table 3-8 Study VX16-445-001: Schedule of Assessments for Part F (if Conducted)

Event/Assessment ^a	Screening	Treatment Period: Period 1				ETT Visit ^b	Safety Follow-up 28 (± 7) Days After Last Dose
	Days -28 to -1	Day 1 ^c	Day 8 ^d (± 1 day)	Day 15 (± 2 days)	Day 29 (± 2 days)		
Informed consent	X						
Randomization ^e		X					
Demographics	X						
Medical history	X						
CFQ-R ^{f,g}		X		X	X		
Weight ^h	X	X		X	X	X	X
Height ^h	X						
Vital signs ⁱ	X	X		X	X	X	X
Pulse oximetry ⁱ	X	X		X	X	X	X

^a All assessments will be performed before dosing, unless noted otherwise. Assessments that are collected before and after dosing will only be collected once if study drug is not administered on the day of the visit (i.e., if subject prematurely discontinued study drug treatment).

^b If the subject prematurely discontinues study drug treatment, an ETT Visit should be scheduled as soon as possible after the decision to terminate study drug treatment. Subjects who prematurely discontinue treatment will be required to complete the Safety Follow-up Visit. If the ETT Visit occurs 3 or more weeks after the last dose of study drug, the ETT Visit will replace the Safety Follow-up Visit, and a separate Safety Follow-up Visit will not be required.

^c To be eligible to continue into the Treatment Period, subjects must have stable CF disease and have remained on stable CF medication regimen during the 28 days before the Day 1 Visit AND must not have had an acute non-CF illness within 14 days before the Day 1 Visit. See [Section 9.1.2.4](#).

^d The laboratory assessment may be collected at the clinic, at a local laboratory, or during a visit by a qualified individual (e.g., home nurse). If the laboratory assessment is not collected at the clinic, a telephone call to the clinic is required for the collection of AEs. When the laboratory assessment is done in the clinic, the AE collection will also occur in the clinic.

^e Randomization may occur on the previous day (Day -1 Visit) after all inclusion and exclusion criteria have been confirmed.

^f CFQ-R must be completed before the start of any other assessments scheduled at that visit.

^g The predose assessment on the Day 1 Visit may be performed on the previous day (Day -1 Visit) if randomization has occurred.

^h Weight and height will be measured with shoes off.

ⁱ Vital signs and pulse oximetry will be collected after the subject has been seated for at least 5 minutes.

Table 3-8 Study VX16-445-001: Schedule of Assessments for Part F (if Conducted)

Event/Assessment ^a	Screening	Treatment Period: Period 1				ETT Visit ^b	Safety Follow-up 28 (± 7) Days After Last Dose
	Days -28 to -1	Day 1 ^c	Day 8 ^d (± 1 day)	Day 15 (± 2 days)	Day 29 (± 2 days)		
Physical examination ^j	Complete	Abbrev.		Abbrev.	Abbrev.	Abbrev.	Complete
Standard 12-lead ECG ^k	X	X		X	X	X	X
Sweat chloride ^{g, l}	X	X		X	X	X	X
Spirometry ^m	X ⁿ	X		X	X	X	X
Urinalysis ^g	X	X		X	X	X	X
Pregnancy test (all females of childbearing potential)	Serum	Urine			Urine	Serum	Serum
CFTR genotype ^o	X						
FSH ^p	X						
G6PD activity test ^q	X						
Serum chemistry and hematology ^g	X	X	X	X	X	X	X

^j Complete and abbreviated PEs are described in [Section 11.7.3](#). Symptom-targeted PEs will occur at any time during the study if triggered by AEs or if deemed necessary by the investigator or healthcare provider.

^k All standard 12-lead ECGs will be performed after the subject has been seated or supine for at least 5 minutes. On the Day 1 and 15 Visits, ECGs will be collected before dosing and 5 hours (± 1 hour) after dosing. At all other visits, ECGs will be collected before dosing (as applicable). ECGs collected on the Day 1 Visit before dosing will be performed in triplicate.

^l Sweat chloride will be measured in all subjects as described in [Section 11.4.1](#). If the value cannot be determined from the screening test, a sweat chloride value documented in a previous laboratory report may be used to establish eligibility. See [Section 8.2.1](#) (Inclusion Criterion #5) for additional detail.

^m Spirometry may be performed pre- or post-bronchodilator at the Screening Visit. Spirometry will be performed pre-bronchodilator, before the morning dose of study drugs, and should be performed at approximately the same time at every visit. On the Day 1 and 15 Visits, spirometry will also be performed pre-bronchodilator, 5 hours (± 1 hour) after study drug administration.

ⁿ The ppFEV₁ assessment that will be used for stratification of randomization can be done any time during the Screening Period. See [Section 9.1.2.2](#).

^o *CFTR* genotyping will be performed for all subjects. If the screening *CFTR* genotype result is not received before randomization, a previous *CFTR* genotype laboratory report may be used to establish eligibility. However, as outlined in [Section 9.9](#), subjects who have been randomized and whose screening *CFTR* genotype does not confirm study eligibility must be discontinued from the study, even if a previous *CFTR* genotype laboratory report was used to establish eligibility.

^p FSH will be measured for any potential postmenopausal female subjects with at least 12 months of continuous spontaneous amenorrhea.

^q Blood samples will be collected for the G6PD activity test.

Table 3-8 Study VX16-445-001: Schedule of Assessments for Part F (if Conducted)

Event/Assessment ^a	Screening	Treatment Period: Period 1				ETT Visit ^b	Safety Follow-up 28 (± 7) Days After Last Dose
	Days -28 to -1	Day 1 ^c	Day 8 ^d (± 1 day)	Day 15 (± 2 days)	Day 29 (± 2 days)		
Coagulation ^e	X	X		X	X	X	X
PK sampling ^g		X		X	X	X	
VX-445/TEZ/VX-561 or placebo dosing ^t		Day 1 through Day 29					
AEs, medications ^u , treatments, and procedures	Continuous from signing of the ICF through the Safety Follow-up Visit						

AE: adverse event; CF: cystic fibrosis; CFQ-R: Cystic Fibrosis Questionnaire-Revised; *CFTR*: CF transmembrane conductance regulator gene; ████████████████████ ECG: electrocardiogram; ETT: early termination of treatment; FSH: follicle-stimulating hormone; G6PD: glucose-6-phosphate dehydrogenase; ICF: informed consent form; IVA: ivacaftor; PE: physical examination; PK: pharmacokinetic; ppFEV₁: percent predicted forced expiratory volume in 1 second ; TEZ: tezacaftor

- ^s Blood samples will be collected for PK analysis of VX-445, TEZ, M1-TEZ, and VX-561. On the Day 1 Visit, samples will be collected before dosing (0 hours) and at 1, 2, 4, and 6 hours after dosing (relative to the morning dose). On the Day 15 Visit, samples will be collected before dosing (0 hours) and at 1, 2, 4, 6, and 8 hours after dosing. On the Day 29 Visit, a predose sample will be collected before the morning dose of study drug. At the ETT visit, a single blood sample for PK analysis will be collected.
- ^t On days of scheduled visits, the in-clinic dose of study drugs will be given in the morning, at least 6 hours apart from any other scheduled dose and after all predose assessments are complete. The last dose of VX-445/TEZ/VX-561 or placebo will be the morning dose on the Day 29 Visit. See [Section 9.6.2](#) for additional information about study drug administration.
- ^u Refer to [Section 9.5.2](#) for details.

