^c A standard 12-lead ECG will be performed after the subject has been seated or supine for at least 5 minutes (Section 11.7.5.1).

^d A single blood sample will be collected from all subjects for the G6PD activity test.

^e Following at least a 4-hour fast, blood samples will be collected for clinical laboratory assessments.

Table 3-2 Study VX16-445-001: Part A, Cohorts A1 Through A6, Treatment Period and Safety Follow-up Visit

Event/Assessment ^a	Study Day						Safety Follow-up Visit (7 to 10 days After Last Dose of Study Drug)
	-1	1	2	3	4	5	
Inpatient days	X	X	X	X	X	X ^b	
Outpatient visit							X
Randomization		X					
Weight ^c	X						
Continuous ECGs ^d		X	X				
Standard 12-lead ECG ^e	X	X					X
Vital signs ^f	X	X	X	X	X	X	X
Full PE	X						X
Serum chemistry	X		X				X
Hematology	X		X				X
Blood for PK analysis ^g		X	X	X	X	X	
Drug test (urine or blood), including cotinine	X						
Alcohol test (urine, blood, or breath)	X						
Urinalysis							X
Study drug administration ^h		X					
AEs	Continuous from signing of ICF through Safety Follow-up Visit						
Medications review ⁱ	Continuous from signing of ICF through Safety Follow-up Visit						

AE: adverse event; CRU: clinical research unit; ECG: electrocardiogram; ICF: informed consent form; PE: physical examination; PK: pharmacokinetic

^a On dosing days, assessments will be performed before dosing, unless noted otherwise.

^b Subjects will be discharged from the CRU on Day 5 after completion of the study visit assessments.

^c Weight will be measured with shoes off.

^d Continuous ECGs will be extracted in up to 10 replicates on Day 1 before dosing (at -60, -50, and -40 minutes) and at 1, 2, 3, 4, 6, 8, 12 and 24 hours (Day 2) after dosing. Subjects should be supine or semi-recumbent for at least 15 minutes before these time points.

^e Standard 12-lead ECGs will be performed after the subject has been seated or supine for at least 5 minutes. On Day 1, ECGs will be collected before dosing and approximately 1, 3, 5, and 6 hours (± 15 min) after dosing.

^f Vital signs will be performed after the subject has been seated for at least 5 minutes.

^g Blood samples for PK assessments will be collected on Day 1 before dosing (0 hours) and at 0.5, 1, 1.5, 2, 3, 4, 5, 6, 8, 12, 24 (Day 2), 36 (Day 2), 48 (Day 3), 72 (Day 4), and 96 (Day 5) hours after dosing. Acceptable PK sampling windows are provided in [Table 11-1](#).

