^h Study drug will be administered in the fed state. Details are provided in [Section 9.6.1.1](#).

ⁱ All medications taken from 28 days before the first dose of study drug through the end of the study will be recorded.

Table 3-3 Study VX16-445-001: Part A, Cohort A7, Treatment Period and Safety Follow-up Visit

Event/ Assessment ^a	Study Day																	Safety Follow-up Visit (7 to 10 Days After Last Dose of Study Drug)	
	-1	1	2	3	4	5	6	7	8	9	10	11	12	13	14 ^b	15 ^b	16 ^b		17 ^b
Inpatient days	X	X	X	X	X	X	X	X	X	X	X	X	X	X ^c	X	X	X	X ^d	
Outpatient visit																			X
Weight ^e	X																		
Standard 12-lead ECG ^f	X	X						X						X					X
Vital signs ^g	X	X	X	X	X	X	X	X	X	X	X	X	X	X	X	X	X	X	X
Full PE	X																		X
Serum chemistry	X		X						X						X				X
Hematology	X		X						X						X				X

^a On dosing days, assessments will be performed before dosing, unless noted otherwise.

^b If data to support use of the IV dose is not available, Dosing Period 3 will not be conducted and assessments on Days 14 to 17 will not be performed.

^c Subjects will be discharged from the CRU on Day 13 after completion of the study visit assessments if Dosing Period 3 is not conducted.

^d Subjects will be discharged from the CRU on Day 17 after completion of the study visit assessments.

^e Weight will be measured with shoes off.

^f Standard 12-lead ECGs will be performed after the subject has been seated or supine for at least 5 minutes. On Days 1, 7 and 13, ECGs will be collected before dosing and approximately 1, 3, 5, and 6 hours (± 15 min) after dosing.

^g Vital signs will be performed after the subject has been seated for at least 5 minutes.

Table 3-3 Study VX16-445-001: Part A, Cohort A7, Treatment Period and Safety Follow-up Visit

Event/ Assessment ^a	Study Day																	Safety Follow-up Visit (7 to 10 Days After Last Dose of Study Drug)	
	-1	1	2	3	4	5	6	7	8	9	10	11	12	13	14 ^b	15 ^b	16 ^b		17 ^b
Blood for PK analysis ^h		X	X	X	X	X	X	X	X	X	X	X	X	X ⁱ	X	X	X	X	
Drug test (urine or blood), including cotinine	X																		
Alcohol test (urine, blood, or breath)	X																		
Urinalysis																			X
Study drug administration ^j		X						X						X ^k					
AEs	Continuous from signing of ICF through Safety Follow-up Visit																		
Medications review ^l	Continuous from signing of ICF through Safety Follow-up Visit																		

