	Days -28 to -1	Day 1 ^c	Day 8 for Part D1 only (± 1 day)	Day 15 (± 2 days)	Day 29 (± 2 days)	Period 2 Visit ^d		
Informed consent	X							
Randomization ^e		X						
Demographics	X							
Medical history	X							
CFQ-R ^{f,g}		X		X	X			
Weight ^h	X	X	X	X	X		X	
Height ^h	X							
Vital signs ⁱ	X	X	X	X	X	X	X	
Pulse oximetry ⁱ	X	X	X	X	X	X	X	

^a All assessments will be performed before dosing, unless noted otherwise. Assessments that are collected before and after dosing will only be collected once if study drug is not administered on the day of the visit (i.e., if subject prematurely discontinued study drug treatment).

^b If the subject prematurely discontinues study drug treatment, an ETT Visit should be scheduled as soon as possible after the decision to terminate study drug treatment. Subjects who prematurely discontinue treatment will be required to complete the Safety Follow-up Visit. If the ETT Visit occurs 3 or more weeks after the last dose of study drug, the ETT Visit will replace the Safety Follow-up Visit, and a separate Safety Follow-up Visit will not be required.

^c To be eligible to continue into the Treatment Period, subjects must have stable CF disease and have remained on stable CF medication regimen during the 28 days before the Day 1 Visit AND must not have had an acute non-CF illness within 14 days before the Day 1 Visit. See [Section 9.1.2.4](#).

^d The Period 2 Visit will occur 6 to 10 days after the actual date of the Day 29 Visit.

^e Randomization may occur on the previous day (Day -1 Visit) after all inclusion and exclusion criteria have been confirmed.

^f CFQ-R must be completed before the start of any other assessments scheduled at that visit.

^g The predose assessment on the Day 1 Visit may be performed on the previous day (Day -1 Visit) if randomization has occurred.

^h Weight and height will be measured with shoes off.

ⁱ Vital signs and pulse oximetry will be collected after the subject has been seated for at least 5 minutes.

Table 3-6 Study VX16-445-001: Schedule of Assessments for Parts D1 and D2

Event/Assessment ^a	Screening	Treatment Period					ETT Visit ^b	Safety Follow-up 28 (± 7) Days After Last Dose
		Period 1			Period 2			
	Days -28 to -1	Day 1 ^c	Day 8 for Part D1 only (± 1 day)	Day 15 (± 2 days)	Day 29 (± 2 days)	Period 2 Visit ^d		
Physical examination ^j	Complete	Abbrev.		Abbrev.	Abbrev.		Abbrev.	Complete
Standard 12-lead ECG ^k	X	X	X	X	X		X	X
Sweat chloride ^{g,l}	X	X	X	X	X	X ^m	X	X

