7 STUDY ENDPOINTS

7.1 Primary Endpoints

Parts A, B, and C: Safety and tolerability, based on the assessment of adverse events (AEs), clinically significant laboratory test results, standard 12-lead electrocardiograms (ECGs), vital signs, and spirometry (Parts B and C only)

Parts D, E, and F:

- Safety and tolerability assessments of AEs, clinical laboratory values, standard 12-lead ECGs, vital signs, pulse oximetry, and spirometry
- Absolute change in percent predicted forced expiratory volume in 1 second (ppFEV₁) from baseline through Day 29

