9.1.1 Parts A, B, and C

Parts A, B, and C are randomized, double-blind, placebo-controlled, single- and multiple-dose parts in healthy subjects of this first-in-human study of VX-445. Part A also includes an evaluation of the effect of food on VX-445 PK and an evaluation of absolute BA. Part C doses VX-445 in TC with TEZ/IVA.

There is no pre-specified ratio of males to females, but reasonable effort will be made to enroll females of non-childbearing potential in all dosing cohorts.

Parts A, B, and C (Healthy Subjects)

A schematic of the study design for Parts A, B, and C is shown in [Table 9-1](#).

Number of Cohorts

In Parts A and B, 6 dose escalation cohorts are planned, although fewer than 6 or up to 2 additional cohorts may be enrolled in each part, based on data from previous cohorts. The additional cohorts will follow the corresponding schedule of assessments. In Part C, 2 cohorts are planned, while fewer or up to 2 additional cohorts each may be enrolled based on data from previous cohorts. The decision to initiate successive cohorts and dose selection will be based on safety, tolerability, and available PK data from preceding cohort(s). Refer to [Section 9.7.1](#) for dose escalation criteria and [Section 9.8.1](#) for stopping criteria.

Staggering of Dosing

In Cohort A1 (first single dose cohort) and in Cohort C1 (first TC cohort), dosing will be staggered so that 2 subjects are dosed (Cohort A1: 1 with VX-445 and 1 with placebo; Cohort C1: 1 with TC and 1 with triple placebo) at least 24 hours before the remaining 6 subjects in each cohort. Doses may be staggered in other cohorts if deemed necessary based on review of emerging safety data.

Timing of Part B and C Initiation

Part B may be initiated while Part A is ongoing after review of safety, tolerability, and PK data.

[figure not shown]
Part C may be initiated while Parts A and B are ongoing after review of safety, tolerability, and PK data.

Starting Dose in Parts B and C

Information about the starting doses of Cohorts B1 and C1 can be found in [Table 9-1](#) and [Section 9.3.2.1](#).

Table 9-1 Study Design for Parts A, B, and C

Part A: Single-dose escalation of VX-445
 Cohorts A1 to A6: 8 subjects per cohort, randomized 3:1 (VX-445:placebo). Planned doses are shown; doses may be modified upward or downward based on emerging data.

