11.7.4 Pulse Oximetry (Parts D, E, and F)

Arterial oxygen saturation by pulse oximetry will be measured after at least a 5-minute rest (seated) and before study drug dosing. At visits when study drug is taken at the site, pulse oximetry will be collected before the morning dose. This is a noninvasive measure of oxygen delivery to the tissues and has been correlated with clinical status and lung function.

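### Vital signs are a primary safety endpoint in every part, yet all scheduled dosing-day readings are pre-dose, so blood pressure, temperature and respiration are not scheduled in the hours after a dose

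*Protocol*

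**What the plan says.** Protocol Section 7.1 makes vital signs part of the primary safety endpoint for Parts A to C. For Parts D to F it lists: "Safety and tolerability assessments of AEs, clinical laboratory values, standard 12-lead ECGs, vital signs, pulse oximetry, and spirometry".

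The timing rule is in Protocol Section 3. For Parts A to C, footnote a of Tables 3-2 to 3-5 reads: "On dosing days, assessments will be performed before dosing, unless noted otherwise". For Parts D to F, footnote a of Tables 3-6 to 3-8 reads: "All assessments will be performed before dosing, unless noted otherwise". The vital-signs footnote in Table 3-2 adds only posture and rest: "Vital signs will be performed after the subject has been seated for at least 5 minutes". The corresponding footnotes in the other tables add no time either, and nor does Section 11.7.3. Section 9.6.1 places dosing after the baseline vital signs. Section 11.7.4 says that oxygen saturation "will be measured after at least a 5-minute rest (seated) and before study drug dosing".

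Where a post-dose time is wanted, it is written out. For Cohort A7, Table 3-3 says: "On Days 1, 7 and 13, ECGs will be collected before dosing and approximately 1, 3, 5, and 6 hours". Tables 3-4 and 3-5 give spirometry at 6 hours, and Tables 3-6 to 3-8 give ECG and spirometry at 5 hours on Days 1 and 15. Note b to Table 11-4 of the Parts D to F SAP confirms that target times are pre-dose for everything except ECG and spirometry.

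**The concern.** The sponsor will draw a conclusion about vital signs from a schedule that never looks in the hours after a dose. This matters most in the first-in-human dose-escalation parts, where it feeds the judgement that a dose was safe and well tolerated. Protocol Section 9.3.2.2 builds the Part D doses on that judgement.

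The staggered dosing in Cohorts A1 and C1 shows the gap. The first two subjects are dosed "at least 24 hours before the remaining 6 subjects in each cohort", but no vital signs are scheduled after their first dose until Day 2.

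A short-lived, symptomless change in blood pressure, temperature, respiration or, in Parts D to F, oxygen saturation could occur and resolve before the next reading. The tables would then show no effect because nothing was measured at that time.

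**Working it through.** The plan gives no figure to reproduce. The check is a reading of each schedule and a count per subject.

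**Step 1. Dosing-day readings, Parts A to C.** Inputs are the vital-signs, dosing and standard ECG rows of Tables 3-2 to 3-5 with their footnotes. Each ECG dosing day has 4 post-dose recordings (1, 3, 5 and 6 hours).

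| Schedule | Vital-signs readings on dosing days | Of these, with a post-dose time | Post-dose standard ECGs |
|---|---|---|---|
| A1 to A6 | 1 (Day 1) | 0 | 1 × 4 = 4 |
| A7 | 3 (Days 1, 7, 13) | 0 | 3 × 4 = 12 |
| B | 10 (Days 1 to 10) | 0 | 2 × 4 = 8 (Days 1, 5) |
| C | 14 (Days 1 to 14) | 0 | 2 × 4 = 8 (Days 1, 7) |
| Sum | 1 + 3 + 10 + 14 = 28 | 0 | 4 + 12 + 8 + 8 = 32 |

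In Cohorts A1 to A6, the first 12 hours after the dose contain 10 PK samples (0.5, 1, 1.5, 2, 3, 4, 5, 6, 8 and 12 hours), 4 standard ECGs and 0 scheduled vital signs.

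**Step 2. Parts D, E and F.** On Days 1 and 15 the subject has ECG and spirometry at 5 hours, and on Day 15 PK sampling runs to 8 hours. Vital signs and oximetry have no post-dose time at any visit.

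**Step 3. First scheduled vital signs after dosing starts.**
- A1 to A6: Day 2, no clock time given.
- A7, after the infusion: Day 14. The infusion on Day 13 lasts 30 minutes, PK is drawn at 0.5 hours and the first post-dose ECG is at 1 hour.
- B and C: Day 2, before the next morning dose.
- D1: Day 8. D2 and F: Day 15.
- E: Day 15 for VX-445; the Day 1 reading already follows TEZ/IVA given in the run-in.

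**Step 4. What reaches the tables.** For Parts A to C, Protocol Section 12.3.5.4.1 and Section 9.3.4 of the A to C SAP summarise vital signs at scheduled time points. Section 9.1 of that SAP only lists unscheduled values, apart from the ECG maxima and the derivation of baseline. For Parts D to F, Section 8.1 of the SAP lets unscheduled values enter visit windows and on-treatment extremes. Section 8.4.4 applies the blood-pressure thresholds of Table 11-10, but every scheduled dosing-day value behind them is pre-dose.

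**Step 5. Relation to peak exposure.** The documents give no Tmax for VX-445. If the oral peak falls in the sampled hours after dosing (0.5 to 12 in Parts A to C, 1 to 8 in Parts D to F), no scheduled reading is near it. For the infusion, the peak is expected at about its end, and the next scheduled reading is on the following day.

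**The case against.** The strongest reply is that the pre-dose timing is deliberate and consistent: the schedules, Section 11.7.4 and SAP Table 11-4 agree. Whether post-dose blood pressure is needed may also depend on nonclinical data that the public text does not show. This stands to the extent that the point is a design improvement and not an internal contradiction.

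A reader might infer more than the documents support:

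- **That heart rate after dosing is missed.** It is not. It is taken with every post-dose ECG and tabulated by time point (Protocol Sections 12.3.5.3.1 and 12.3.5.3.2), and Cohorts A1 to A6 also have continuous ECG extractions to 24 hours.
- **That all readings are troughs at the lowest exposure.** A single dose in Part A has no dosing interval. Part B Days 11 to 14 and Part C Days 15 to 18 follow the last dose. In Parts B to F, later pre-dose readings are still taken on treatment.
- **That no part can detect an effect.** Section 11.7.3 allows symptom-directed readings, and clinically significant worsening becomes an adverse event. The first two subjects in A1 and C1 are inpatients with four post-dose ECGs on Day 1, serial PK sampling and continuous adverse-event collection. These safeguards do not pick up a change without symptoms.

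Two practical objections also stand. Vital signs are taken seated, whereas in Cohorts A1 to A6 the subject should be supine or semi-recumbent for at least 15 minutes before the continuous-ECG times, which include 1, 3 and 6 hours. During the Cohort A7 infusion the subject is supine. Added readings therefore need sequencing. Also, Section 9.3.2.2 already reports results for single doses to 360 mg (Part A) and multiple doses to 340 mg (Part B) and 280 mg (Part C), so a schedule change comes too late for those cohorts.

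**Conclusion.** The point holds in this form. Vital signs are in the primary safety endpoint of every part, but no part schedules blood pressure, temperature or respiration rate, or in Parts D to F oxygen saturation, in the hours after a dose. In Parts A to C, 0 of 28 scheduled dosing-day readings per set of schedules are post-dose; in Parts D to F there are none at any visit.

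The consequence is limited: a symptomless change in those measures during the hours after dosing would not be seen in the summaries. Placing the gap at peak exposure is an assumption for oral doses, because no Tmax is given; for the infusion it rests on the expected profile. The documents do not show that any such effect exists, and they do not support a claim that cardiovascular monitoring after dosing is absent.

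**What to change.** 1. **Parts D, E and F.** In Tables 3-6 to 3-8 and Section 11.7.4, add seated vital signs and pulse oximetry at the existing 5-hour ECG and spirometry time on Days 1 and 15. Summarise them by time point in SAP Sections 8.4.4 and 8.4.5. Give them their own nominal-visit rows in SAP Table 11-4, as for ECG. Otherwise the rule that takes the latest of several readings equally far from the target day would let the 5-hour value on Day 15 replace the pre-dose value.
2. **Any Part A, B or C cohort still to be dosed.** Add vital signs around the existing post-dose ECG times, and after the end of the infusion in Cohort A7. State the posture, the same at baseline and after dosing, and the order relative to the continuous-ECG rest period and the PK draws, whose window is ±5 minutes up to 12 hours.
3. **Cohorts already dosed.** State in the Parts A to C SAP and in the report that scheduled vital signs do not cover the first hours after dosing, and limit the conclusion to match.

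The cost is a few minutes per time point, some sequencing in Part A and more rows in the vital-signs tables. No new visit, staff or equipment is needed.
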